## **1.5 Statistical analyses**

All statistical methods will be detailed in a statistical analysis plan (SAP). The SAP will be finalized prior to database lock and unblinding.

### **1.5.1 Sample size rationale**

Effect size estimates were based on relevant literature and the results of available MTX-071-P03 trial results utilizing the absolute change from baseline to Week 12 endpoint. A total number of 382 subjects are required to achieve an overall power of at least 90% to reject the null hypothesis of no treatment difference in treatment group means between RTX-GRT7039 and placebo (2-sided t-test, type I error of  $\alpha = 0.05$ ). This is based upon an expected treatment difference of at least 1 point on 11-point (0-10) NRS (absolute change from baseline in the WOMAC pain subscale score) on the primary efficacy endpoint and a standard deviation of 3 in both treatment groups.

To be able to conduct confirmatory testing for the secondary endpoints, an alpha-adjustment will need to be taken into consideration. The sample size is, therefore, expected to be approximately 450 subjects (225 receiving placebo and 225 receiving RTX-GRT7039).

Assuming a screening failure rate of about 40%, approximately 750 subjects are planned to be screened to randomize 450 subjects for the primary analysis (225 evaluable subjects for the RTX-GRT7039 treatment arm, and 225 for the placebo arm, 1:1 randomization).

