### Full Analysis Set

All randomly assigned subjects with at least 1 IMP administration (including incomplete administrations)

Analyses on the Full Analysis Set (FAS) will be conducted based on the treatment as randomized (i.e., based on planned treatment).

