#### 1.5.3 Statistical methods and analysis

To evaluate the primary endpoint, the WOMAC pain subscale with a 48 hour recall period will be assessed weekly using e-diaries. The WOMAC pain subscale is comprised of 5 questions regarding the amount of pain experienced due to osteoarthritis in the index knee in the past 48 hours using an 11-point (0-10) NRS. The WOMAC pain subscale score is calculated as the mean of the scores from the 5 individual questions, which may not be a whole (integer) number. The baseline WOMAC pain subscale score is defined as the assessment made at the Randomization Visit (V2).

The estimand of interest for the primary efficacy analysis is the difference in mean change from baseline in 48-hour WOMAC pain subscale at Week 12 in the index knee using an 11-pt NRS (0-10) between RTX-GRT7039 and placebo, in subjects who initiate treatment, as if substantial changes in background medication or addition of new analgesics were not available.

The primary efficacy analysis will be performed using a mixed-effects model for repeated measures (MMRM). The model will include fixed effects of treatment, country/region, gender, time (corresponding to trial week), and treatment-by-time interaction. The baseline value will be a covariate. Time will be included in the MMRM analysis to account for the correlation in repeated measures within-subject. An unstructured [UN] covariance matrix will initially be fitted to the MMRM. If the analysis model does not converge, then the Toeplitz [TOEP] will be used as the covariance matrix. The auto-regressive (1) [AR(1)] covariance matrix will be used if TOEP also fails to converge. In the event that AR(1) also results in non-convergence, the compound symmetry covariance matrix [CS] will be used.

Individual sites will be pooled by geographic region. Geographic regions will be defined in the SAP and correspond to the country/region used in the stratified randomization.

For the primary analysis the following intercurrent events will be considered:

- A substantial change in the analgesic osteoarthritis background therapy (optimal SOC) will be considered as an intercurrent event. For this, a hypothetical policy estimand strategy is applied. Values after the occurrence of the intercurrent event will be excluded from the analyses and will be imputed by the baseline value.

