**Grünenthal**  
Confidential

Protocol KF7039-02

Page 16 of 78  
DMS version 3.0  
03 Dec 2021

Trial Period	Screening Period	Treatment and Follow-up Period						
		Visit	V1 (Screening Visit)	V2 a (Randomization Visit)	V3 ± 3 days	V4 ± 3 days	V5 ± 3 days	V6 ± 3 days
Day	-30 to -1	1	8	29	85	183	267	365
Week			1	4	12	26	38	52
SF-36		X			X	X	X	X
TSQM					X	X	X	X
Randomization to treatment		X						
Pre-treatment with ropivacaine intra-articular injection		X						
Collect urine and perform pregnancy (if applicable) and drugs of abuse testing	X	X						
Safety laboratory	X	X				X		X
Intra-articular IMP injection		X						
Ask subjects to rate their procedural pain k		X						
Record adverse events l	X	X	X	X	X	X	X	X
Collect e-diary								X
Collect subject trial card								X

a) All other assessments are completed prior to IMP administration, assessment of procedural pain, and recording of adverse events.

b) Subjects who discontinue or who are discontinued earlier from the trial will have the Final Visit/Early Termination Visit as a last trial visit, if possible.

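### Does the step from 382 to about 450 subjects leave the trial without an allowance for lost data?

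*Combined protocol and SAP*

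**What the plan says.** Section 1.5.1 of the protocol synopsis builds the sample size in three steps.

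- The base calculation: "A total number of 382 subjects are required to achieve an overall power of at least 90" per cent, using a two-sided t-test at 0.05, a difference of 1 point on the 0-10 scale and an SD of 3 in each arm.
- The increase: for confirmatory testing of secondary endpoints, "an alpha-adjustment will need to be taken into consideration", followed by "The sample size is, therefore, expected to be approximately 450 subjects". The adjusted alpha and the method are not given.
- The screening step: with about 40% screening failures, some 750 are screened to "randomize 450 subjects for the primary analysis (225 evaluable subjects for the RTX-GRT7039 treatment arm, and 225 for the placebo arm, 1:1 randomization".

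Other parts of the synopsis bear on this. The Full Analysis Set in Section 1.5.2 is "All randomly assigned subjects with at least 1 IMP administration (including incomplete administrations"). A footnote to the Schedule of events (Section 1.6) provides for early leavers: "Subjects who discontinue or who are discontinued earlier from the trial will have the Final Visit/Early Termination Visit" as their last visit. Section 1.5.3 specifies a mixed model for repeated measures and adds "The baseline value will be a covariate". It also replaces values after a substantial change in osteoarthritis background therapy with the baseline value. Section 1.5 defers detail: "All statistical methods will be detailed in a statistical analysis plan (SAP").

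**The concern.** The alpha adjustment is the only reason given for the extra 68 subjects, and its size is not stated. The same 450 are then described both as randomized and as evaluable. The one attrition rate in the section, 40%, applies before randomization. A reader who expects the usual chain (evaluable number, divided by one minus the loss rate, gives the number to randomize) finds the last link missing, although the Schedule of events foresees early termination.

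If the alpha adjustment really uses up all 68 subjects, any missing Week 12 data would take power for the primary comparison below 90%. If the primary keeps the full 0.05, the same 68 subjects act as a sizeable reserve. The section does not say which applies, so the 450 looks as though it might be too small.

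**Working it through.** **Inputs.** From Section 1.5.1: difference 1, SD 3, 1:1 allocation, two-sided t-test, alpha 0.05, power at least 90%, totals 382 and 450, screening failure 40%. Assumed, because the synopsis gives no figure: any alpha other than 0.05, every loss rate, the baseline correlation, the share of subjects imputed and the mean placebo improvement.

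**1. Reproduce the stated figures.** With n per arm, the noncentrality is 1 / (3 × √(2/n)) on 2n − 2 degrees of freedom.

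- n = 190: noncentrality 3.249, power 89.99%.
- n = 191: noncentrality 3.258, power 90.13%. The total is 2 × 191 = 382, as stated.
- Screening: 450 / (1 − 0.40) = 750, as stated.

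**2. What 450 buys, by alpha.** With n = 225 the noncentrality is 3.536.

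| Two-sided alpha for the primary | Total for 90% power | Power of 450, no loss | Room for loss, 1 − total/450 |
|---|---|---|---|
| 0.05 (stated) | 382 | 94.2% | 15.1% |
| 0.04 (assumed) | 404 | 93.0% | 10.2% |
| 0.03 (assumed) | 432 | 91.2% | 4.0% |
| 0.025 (assumed) | 450 | 90.0% | none |

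At 0.025, 224 per arm gives 89.91% and 225 gives 90.05%, so halving alpha reproduces 450 exactly. But 382 / 0.85 = 449.4 also rounds up to 450. The number alone does not reveal which calculation produced it.

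**3. Power of 450 if some subjects contribute nothing (assumed rates).** The effective n per arm is 225 × (1 − loss).

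| Loss | n per arm | Power at 0.05 | Power at 0.025 |
|---|---|---|---|
| 5% | 213.75 | 93.0% | 88.4% |
| 10% | 202.5 | 91.7% | 86.5% |
| 15% | 191.25 | 90.2% | 84.3% |
| 20% | 180 | 88.4% | 81.9% |

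**4. Offset from the baseline covariate.** The residual SD is 3 × √(1 − r²), where r is the correlation of baseline with change. For r = 0.3 to 0.4 (assumed) at alpha 0.025, power is 91.3-93.4% with 5% loss, 89.7-92.0% with 10% and 87.8-90.4% with 15%. The covariate therefore recovers most or all of the shortfall even at the halved alpha.

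**5. An effect in the other direction.** Subjects given the baseline value are not removed; they enter with zero change. Suppose a share q of each arm is imputed this way, the other subjects have SD 3, and mean improvement is m on placebo and m + 1 on active. The difference becomes (1 − q) × 1. The variance in an arm with mean improvement μ becomes (1 − q) × 9 + q(1 − q)μ².

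- q = 0.15, m = 1: difference 0.85, variances 7.78 and 8.16, noncentrality 0.85 / √((7.7775 + 8.16)/225) = 3.194, power 89.0% at 0.05.
- q = 0.15, m = 3: variances 8.80 and 9.69, noncentrality 2.965, power 84.1%.
- q = 0.10, m = 1 to 3: power 91.0% to 88.0%.

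The 15.1% in step 2 is therefore room for removed subjects only. It does not cover 15% of subjects imputed at baseline.

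**The case for a change.** The strongest case for acting is that the sponsor's own stated reason, combined with a single natural halving of alpha, lands on exactly 450. On that reading no subject may be lost without dropping below 90%, and a published rationale ought to let a reader see whether that is so. *Evaluable* is undefined, and membership of the Full Analysis Set does not supply the Week 12 value that the planning t-test assumes for each subject. Filling these gaps would cost only wording.

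Much of this stands as description. The section does not show how 382 becomes 450, gives no rate of loss after randomization, and leaves *evaluable* open. It does not stand as evidence of a fault in the design:

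- The alpha of 0.025 is inferred from the arithmetic. The adjustment is tied to the secondary endpoints, so the larger size may instead support those tests while the primary keeps 0.05.
- Randomization and the single injection both take place at Visit 2, and the Full Analysis Set is everyone randomized and dosed. On that natural reading, randomized and evaluable almost coincide.
- The early-termination footnote is routine and covers the whole 52 weeks. It says nothing about loss by Week 12.
- The available text is an extract of a longer protocol, and the SAP was not available. The multiplicity method and loss assumption may be stated in either.

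The obvious rewording, that 450 randomized allows about 15% loss, would itself be unsafe. Step 5 shows power below 90% when 15% of each arm is imputed at baseline.

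**Conclusion.** The concern does not call for a change. No stated figure is wrong: 382 and 750 both reproduce, and the only power the synopsis claims, at least 90% at two-sided 0.05 with 382 subjects, is exceeded by 450 (94.2%) and survives removal of up to 15.1% of them. A shortfall appears only under unstated assumptions. One is an alpha near 0.025 together with real loss: 88.4% at 5% and 86.5% at 10%, before a covariate gain that could restore most or all of it. The other is heavy baseline-value imputation at 0.05: 89.0% to 84.1% with 15% of each arm imputed and placebo improvement of 1 to 3 points.

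What remains is missing detail in a synopsis: the adjusted alpha, the expected rate of missing data and intercurrent events, and the meaning of *evaluable*. A trial statistician would settle these when writing the SAP. Recording them would leave the 450, the primary model and the result as they are. The conclusion rests on the planning values of 1 and 3, and it would need another look if the SAP turned out to test the primary at a reduced alpha while expecting appreciable loss by Week 12.

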### **1.5.2 Subject populations**

#### **Safety Analysis Set**

All subjects with at least 1 IMP administration (including incomplete administrations)

Analyses on the Safety Analysis Set (SAF) will be conducted based on actual treatment received.

### Full Analysis Set

All randomly assigned subjects with at least 1 IMP administration (including incomplete administrations)

Analyses on the Full Analysis Set (FAS) will be conducted based on the treatment as randomized (i.e., based on planned treatment).

#### 1.5.3 Statistical methods and analysis

To evaluate the primary endpoint, the WOMAC pain subscale with a 48 hour recall period will be assessed weekly using e-diaries. The WOMAC pain subscale is comprised of 5 questions regarding the amount of pain experienced due to osteoarthritis in the index knee in the past 48 hours using an 11-point (0-10) NRS. The WOMAC pain subscale score is calculated as the mean of the scores from the 5 individual questions, which may not be a whole (integer) number. The baseline WOMAC pain subscale score is defined as the assessment made at the Randomization Visit (V2).

The estimand of interest for the primary efficacy analysis is the difference in mean change from baseline in 48-hour WOMAC pain subscale at Week 12 in the index knee using an 11-pt NRS (0-10) between RTX-GRT7039 and placebo, in subjects who initiate treatment, as if substantial changes in background medication or addition of new analgesics were not available.

The primary efficacy analysis will be performed using a mixed-effects model for repeated measures (MMRM). The model will include fixed effects of treatment, country/region, gender, time (corresponding to trial week), and treatment-by-time interaction. The baseline value will be a covariate. Time will be included in the MMRM analysis to account for the correlation in repeated measures within-subject. An unstructured [UN] covariance matrix will initially be fitted to the MMRM. If the analysis model does not converge, then the Toeplitz [TOEP] will be used as the covariance matrix. The auto-regressive (1) [AR(1)] covariance matrix will be used if TOEP also fails to converge. In the event that AR(1) also results in non-convergence, the compound symmetry covariance matrix [CS] will be used.

Individual sites will be pooled by geographic region. Geographic regions will be defined in the SAP and correspond to the country/region used in the stratified randomization.

For the primary analysis the following intercurrent events will be considered:

- A substantial change in the analgesic osteoarthritis background therapy (optimal SOC) will be considered as an intercurrent event. For this, a hypothetical policy estimand strategy is applied. Values after the occurrence of the intercurrent event will be excluded from the analyses and will be imputed by the baseline value.
- Any other substantial change in analgesic medication given for any other indication will be considered an intercurrent event. For this, a hypothetical policy estimand strategy is applied. Values after the occurrence of the event will be excluded from the analyses and will be imputed by the last observation.

Sensitivity analyses will be performed.

Subgroup analyses may be considered if appropriate and will be specified in the SAP.

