#### 1.3.1 Inclusion criteria

1. The subject has given written informed consent to participate.
2. The subjects are  $\geq 18$  years of age at the Screening Visit.
3. The subjects have a BMI  $\leq 40.0$  kg/m^2.
4. The subject is willing to adhere to the restricted use of concomitant treatments (see concomitant treatments in Section 1.4.3).
5. The subject has a diagnosis of osteoarthritis of the knee based on American College of Rheumatology criteria and functional capacity class of I-III. Pain at the index knee must be present for at least 6 months prior to Screening Visit.
6. The subject has a Kellgren-Lawrence (KL) grade of 2-4 in the index knee (based on X-ray performed during Screening Visit, assessed by central readers).
7. There is a documented history indicating that subject has insufficient pain relief with optimal standard of care (SoC), i.e.,
  - a. non-pharmacological treatment, and
  - b. 1 or more courses of oral non-steroidal anti-inflammatory drugs (NSAIDs) prescribed by their physician and
  - c. where appropriate, opioids, intra-articular treatment with corticosteroids, and intra-articular treatment with hyaluronic acidin combination or as monotherapies,  
or subject is unable to take SoC due to contraindication or intolerability to 1 or more of the SoC treatments above.  
Further details on the definition of documented history will be provided in the electronic case report form (eCRF) guidance document.
8. The investigator does not consider that any additional benefit can reasonably be expected from further adjustments to the subject's pain treatment.
9. The subject must have a baseline WOMAC pain subscale score  $\geq 5$  on the 11-point (0-10) NRS for the index knee at Screening (assessment in e-diary at V1) and at baseline (assessment in e-diary at V2).
10. Women of child-bearing potential must have a negative pregnancy test at the Screening Visit and prior to the administration of IMP. They must also agree to practice, at a minimum, acceptable measures of birth control for 90 days following administration of IMP.

11. Male subjects must agree to use barrier contraception (condom) during sexual intercourse with women of child-bearing potential after administration of IMP for 90 days. The male subject is willing to ensure that during this period the female sexual partner is additionally practicing contraception, if of childbearing potential.

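### The primary MMRM leaves a small, nearly free gain in precision unused: the V1 pain score and a baseline-by-week term are not in the model

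*Combined protocol and SAP*

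**What the plan says.** Section 1.5.3 lists the fixed effects of the primary MMRM as treatment, country/region, gender, trial week and treatment-by-week. It then says "The baseline value will be a covariate". The same section defines baseline as the one WOMAC pain assessment at the Randomization Visit (V2). No baseline-by-week interaction and no other pre-treatment pain score is listed.

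Inclusion criterion 9 (section 1.3.1) requires an index-knee WOMAC pain score of at least 5 on the 0-10 scale "at Screening (assessment in e-diary at V1) and at baseline (assessment in e-diary at V2"). Exclusion criterion 1 (section 1.3.2) removes anyone scoring 10 at either visit. Every properly enrolled subject therefore has two pre-treatment scores on the scale of the primary endpoint, both between 5 and just under 10.

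Section 1.5.1 sizes the trial by a two-sided t-test at 0.05 and claims no gain from covariates. Section 1.5 defers full methods to a SAP to be finalized before database lock and unblinding.

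**The concern.** A single 48-hour recall measures a subject's usual pain with error. A second score taken at most 30 days earlier carries some of the information that the first one misses.

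A common slope also assumes that baseline predicts the outcome equally well at every week. The plan itself gives one reason why it may not. After a substantial change in osteoarthritis background therapy, values are replaced by the baseline value. For those subjects the score moves one-for-one with baseline, so the pooled slope drifts toward 1 as such events accumulate.

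At stake is a slightly wider interval than necessary at Weeks 12 and 26. This matters most for the alpha-adjusted secondary tests, because section 1.5.1 does not state the adjusted level.

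**Working it through.** **1. The plan's own figure.** Section 1.5.1 states that "A total number of 382 subjects are required to achieve an overall power of at least 90" per cent, for an "expected treatment difference of at least 1 point on 11-point (0-10) NRS" and "a standard deviation of 3 in both treatment groups". The exact two-sample t-test gives 89.99% power at 190 per arm and 90.13% at 191, so 2 × 191 = 382. The figure reproduces.

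**2. Starting point.** The plan raises the size to "approximately 450 subjects (225 receiving placebo and 225 receiving RTX-GRT7039"). With 225 per arm, difference 1 and SD 3, exact power is 94.2% at two-sided 0.05. At an illustrative 0.025 it is 90.0%. Below, SD 3 is taken as the residual SD under the planned covariates (an assumption). A residual-variance cut of g changes the SD to 3 × √(1 − g).

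**3. V1 score, closed form.** Let r be the V1-V2 correlation and ρ the correlation of each with the Week 12 score (both assumed).

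- V2 alone: R² = ρ²
- V1 and V2: R² = 2ρ²(1 − r)/(1 − r²)
- r = 0.5, ρ = 0.3: R² rises from 0.090 to 0.120, so g = (0.120 − 0.090)/(1 − 0.090) = 3.3%. SD becomes 2.950 and power 94.8%.
- r = 0.7, ρ = 0.2: R² rises from 0.040 to 0.047, so g = 0.7%.

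**4. V1 score, with the eligibility range imposed.** This was simulated with both scores limited to 5 to <10. Assumed before restriction: pain mean 6.8, SD 1.8 and follow-up SD 2.8.

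| V1-V2 reliability | Correlation of V2 with follow-up | g | Power, N = 450 |
|---|---|---|---|
| 0.8 | 0.3 | 0.8% | 94.3% |
| 0.5 | 0.3 | 1.9% | 94.5% |
| 0.8 | 0.5 | 2.7% | 94.7% |
| 0.5 | 0.5 | 6.6% | 95.5% |

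The restricted SD of V2 is about 1.2.

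**5. Baseline-by-week term.** Let d be the gap between the Week 12 slope and the common slope, and s the baseline SD. Then g = (d·s)²/[9 + (d·s)²].

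- d = 0.1, s = 1.0: 0.01/9.01 = 0.1%, power 94.2%
- d = 0.3, s = 1.3: 0.152/9.152 = 1.7%, power 94.5%
- d = 0.5, s = 1.3: 0.4225/9.4225 = 4.5%, power 95.1%

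The baseline-imputation rule alone would move the slope by p(1 − b), where p is the share of subjects with an event and b the slope in the others. This takes events as unrelated to baseline. With p from 10% to 30% and b from 0.6 to 0.3 (assumed), the shift runs from 0.10 × 0.4 = 0.04 to 0.30 × 0.7 = 0.21. Even a full gap of 0.21 with s = 1.3 gives only 0.0745/9.0745 = 0.8%.

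**6. Smaller alpha.** At 0.025, g = 6.6% raises power from 90.0% to 92.0%, and g = 4.5% raises it to 91.4%. That is 2.0 and 1.4 points, against 1.3 and 0.9 points at 0.05.

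**The case against.** The strongest reply is that nothing is wrong. Randomization protects the comparison, the sample size does not rely on these terms, and 450 subjects already give 94.2%. Every correlation and slope gap above is assumed, and the 5 to <10 window limits what either score can explain. The supplied text is a synopsis, and the SAP may already contain the terms. All of this stands. It sets the size and scope of the point, but it does not remove a gain from data that are already collected.

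The documents do not support several stronger readings that a reader might infer:

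- **Bias or invalidity.** Omitting prognostic covariates, or using a common slope, does not in itself bias a randomized comparison.
- **No other adjustment.** Country/region and gender are in the model; V2 is only the sole pain covariate.
- **A larger gain.** Setting r = ρ = 0.4 in the closed form gives 8.2%. But then two pre-treatment scores at most 30 days apart would agree no better than baseline and Week 12.
- **KL grade.** Inclusion criterion 6 requires that "The subject has a Kellgren-Lawrence (KL) grade of 2-4 in the index knee", so the grade is available, but nothing in the documents sizes its gain.
- **A V1 function score.** Eligibility uses pain only, and the visible schedule does not confirm that function is recorded at V1.
- **Better handling of dropouts.** Values after the listed intercurrent events are replaced by the baseline or last observation, and covariates do not change those replacements. For other dropouts no gain can be shown.

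**Conclusion.** The point holds as a small missed efficiency in the protocol-level primary model. The V1 score would cut Week 12 residual variance by roughly 1% to 7%, and the baseline-by-week term by roughly 0% to 4.5%. Each is worth about 0 to 1.3 percentage points of power at N = 450 and two-sided 0.05. Even an optimistic combined cut of 10% (SD 2.846) gives 96.1%, or 1.9 points.

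These sizes rest on assumed correlations, slope gaps and baseline SD, on SD 3 as the current residual SD, and on the plan's difference of 1. The 0.025 level is illustrative. The trial does not depend on the change; it is optional and worth making because it costs so little.

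**What to change.** Before unblinding, in section 1.5.3 and the SAP, replace the covariate sentence for the WOMAC pain endpoints with:

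> Covariates are the V2 baseline WOMAC pain score, the baseline-by-week interaction, and the V1 screening WOMAC pain score.

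For the function endpoints, add the baseline-by-week term only.

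**Cost.** For pain, no new data, visits or subjects are needed. The interaction adds one slope for each modelled week beyond the first. If all weekly scores enter, that is 11 extra slopes to Week 12, 25 to Week 26 or 51 to Week 52. V1 adds one parameter. This is affordable with about 450 subjects. Section 1.5.3 does not say which weeks enter the model, so the same edit should state them.

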### **1.3.2 Exclusion criteria**

A single re-screening is accepted for items 4, 5, 6, and 7.

1. The subject reports a WOMAC pain subscale score of 10 on the 11-point (0-10) NRS at Screening (assessment in e-diary at V1) or at baseline (assessment in e-diary at V2) for the index knee.
2. The subject has a WOMAC pain subscale score of  $\geq 4$  on the 11-point (0-10) NRS in the non-index knee at Screening.
3. The subject has past joint replacement surgery of the index knee.
4. The subject had an intra-articular injection of either corticosteroid or intra-articular viscosupplementation (i.e., hyaluronic acid) into the index knee within 90 days of screening.
5. The subject had an injection of platelet-rich plasma or stem cells into the index knee within 6 months of screening.
6. The subject applied topical capsaicin on the index knee within 3 months of Screening.
7. The subject has a history of significant trauma or surgery (e.g., open or arthroscopic) to the index knee within 12 months of Screening.
8. The subject has any known active infection of the index joint, including suspicion of intra-articular infection, ulcer, or open wound anywhere on the index knee.
9. The subject has periarticular pain from any cause other than osteoarthritis, including referred pain, bursitis, or tendonitis.
10. The subject has ipsilateral clinical hip osteoarthritis on the side of the index knee.
11. The subject has pre-existing osteonecrosis, subchondral insufficiency fracture, atrophic osteoarthritis, severe bone on bone osteoarthritis, knee pain attributable to disease other than osteoarthritis, or the subject has rapidly progressing osteoarthritis (RPOA) Type I or Type II.
12. The subject has significant malalignment of anatomical axis (medial angle formed by the femur and tibia) of the target knee (varus  $>10^\circ$ , valgus  $>10^\circ$ ) by X-ray as assessed by independent central readers at Screening Visit.
13. The subject has other conditions that could affect trial endpoint assessments of the index knee, including, but not limited to, rheumatoid arthritis, psoriatic arthritis, ankylosing spondylitis, gout or pseudogout, inflammatory bowel disease related arthropathy, peripheral neuropathy (e.g., diabetic neuropathy), lupus erythematosus, significant skin conditions overlying the index knee, acromegaly, metabolic joint diseases, and fibromyalgia.

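### If the unstructured covariance fails, every named fallback assumes one variance for all modelled weeks; without a robust SE, the Week 12 SE is off when Week 12 variance differs from the fitted pooled variance

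*Combined protocol and SAP*

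**What the plan says.** Section 1.5.3 (Statistical methods and analysis) makes the primary analysis an MMRM on weekly WOMAC pain scores, with treatment-by-time in the mean model and baseline as covariate. UN is fitted first. The fallbacks come in a fixed order:

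- The first step reads: "If the analysis model does not converge, then the Toeplitz [TOEP] will be used as the covariance matrix".
- The second step moves on to a first-order autoregressive structure, should that fit fail as well.
- The last step reads: "In the event that AR(1) also results in non-convergence, the compound symmetry covariance matrix [CS] will be used".

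No heterogeneous-variance version of these structures is listed. The supplied text names no SE type and no degrees-of-freedom method, and does not say which weeks enter the model. Section 1.5 leaves the detail of all methods to a SAP that is to be finalised before database lock and unblinding.

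Three other statements bear on whether weekly variances are equal:

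- The sample size (Section 1.5.1) uses "a standard deviation of 3 in both treatment groups" for the change at Week 12. No SD is given for any other week.
- Baseline pain is bounded by inclusion criterion 9 (at least 5) and exclusion criterion 1 (not 10).
- After a substantial change in osteoarthritis background therapy, values "will be excluded from the analyses and will be imputed by the baseline value" (Section 1.5.3).

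**The concern.** Because the model contains treatment-by-time, the Week 12 estimate is essentially the difference in Week 12 means, whichever covariance is fitted. Its model-based SE is not so protected. Under TOEP, AR(1) or CS, the SE comes from one variance fitted to all modelled weeks together. If Week 12 is more variable than that pooled figure, the SE is too small and the primary test exceeds 5% type I error. If Week 12 is less variable, the SE is too large and some power is lost.

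Nothing in the trial's design assures equal variances across weeks, and the sponsor treats UN failure as possible by listing three fallbacks. The stake is the validity of the single primary test in that situation. A choice of SE method made after the results are known would be open to challenge.

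**Working it through.** **Inputs from the documents.** Difference 1 point, SD 3, two-sided alpha 0.05, 382 subjects required, 225 per arm planned (Section 1.5.1); weekly assessments and the covariance order (Section 1.5.3). **Assumed:** all weekly SD profiles and correlations, because the documents give none.

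**The plan's own figure.** The exact noncentral t gives 90.13% power at 191 per arm and 89.99% at 190, so 382 reproduces. At 225 per arm, power is about 94%.

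**Week 12 SE.** True SE = 3·√(2/225) = 0.2828, ignoring any gain from the baseline covariate. For an assumed true weekly covariance Σ, the large-sample fit of a structure V minimises log|V| + tr(V⁻¹Σ). With r = fitted SD / Week 12 SD, type I error = 2·P(Z > 1.96·r).

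**Hand check with CS.** With complete data, the fitted CS variance is the plain average of the weekly variances. SDs change linearly to 3 at Week 12 and stay flat after that.

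- Weeks 1–12, SD 2.5 to 3: mean variance 7.587; r = √(7.587/9) = 0.918; SE 0.260; type I error 0.072.
- Weeks 1–12, SD 2 to 3: mean variance 6.349; r = 0.840; SE 0.238; type I error 0.10.
- Weeks 1–12, SD 3.5 to 3: mean variance 10.587; r = 1.085; type I error 0.033; power Φ(1/0.2828 − 1.96·1.085) = 0.92 against 0.94.
- Weeks 1–26, SD 2.5 to 3: (12·7.587 + 14·9)/26 = 8.348; r = 0.963; type I error 0.059.
- Weeks 1–52, SD 2.5 to 3: (12·7.587 + 40·9)/52 = 8.674; r = 0.982; type I error 0.054.

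**Type I error over all fallbacks**, complete data, three correlation shapes (exchangeable 0.6; 0.93^lag; 0.45 + 0.35·0.85^lag). The 52-week column covers AR(1) and CS only.

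| SD profile (3.0 at Week 12) | Weeks 1–12 | Weeks 1–26 | Weeks 1–52 |
|---|---|---|---|
| Flat | 0.050 | 0.050 | 0.050 |
| 2.5 to 3, then flat | 0.072 | 0.059–0.063 | 0.054–0.057 |
| 2 to 3, then flat | about 0.10 | 0.069–0.076 | 0.059–0.064 |
| 3.5 to 3, then flat | 0.033 | 0.039–0.042 | 0.043–0.046 |
| Flat to Week 12, then rising to 4 | – | 0.027–0.031 | 0.025–0.026 |

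**Baseline imputation alone** (Weeks 1–12). With share p imputed and mean change −2, variance = (1−p)·9 + p(1−p)·4, with p rising linearly to Week 12. For p = 0.1 at Week 12: 8.10 + 0.36 = 8.46, SD 2.91. For p = 0.2: 7.20 + 0.64 = 7.84, SD 2.80. Type I error is 0.047 and 0.043, on the conservative side.

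**Unequal variances with little harm.** Over Weeks 1–26 with SD 2.5 to 3 to 3.5, r is 1.014–1.015 and type I error 0.047. In a profile where the Week 12 variance equals the 12-week average, r is 1.00 for CS, 0.97 for TOEP and 0.95 for AR(1).

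**Size of the UN matrix.** T(T+1)/2 parameters: 78 for 12 weeks, 351 for 26 and 1378 for 52, with about 450 subjects.

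**Dropout simulation** (225 per arm, REML, about 20% monotone dropout assumed to depend on the last value, third correlation shape, 3,000–4,000 trials, Monte Carlo error about ±0.008). Rejection under no effect:

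| Case | Model-based SE | Sandwich SE |
|---|---|---|
| Weeks 1–12, SD 2.5 to 3, CS | 0.075 | 0.049 |
| Weeks 1–12, SD 2.5 to 3, AR(1) | 0.068 | 0.050 |
| Weeks 1–26, SD 2.5 to 3, CS | 0.066 | 0.054 |
| Weeks 1–26, SD 2.5 to 3, AR(1) | 0.054 | 0.049 |
| SD 3.5 to 3, CS | 0.041 | 0.049 |
| Flat SD, CS | 0.060 | 0.054 |

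The last row reflects a wrong correlation rather than unequal variance, and its two figures differ by less than the Monte Carlo error.

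**The case against.** The strongest reply is that two conditions must both occur, and the documents show neither: UN must fail, and the Week 12 variance must differ from the pooled one. That stands, and no probability of failure can be given. The largest inflation also falls where failure is least likely. The figures of 0.072 and 0.10 belong to a 12-week model, which needs only 78 covariance parameters. With more weeks, UN failure is more plausible, but the same rising profiles then give 0.059–0.076 (26 weeks) and 0.054–0.064 (52 weeks).

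Three stronger readings are tempting, and the documents do not support them.

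- A reader might infer that the Week 12 SE is wrong whenever weekly variances differ. It is off only when Week 12 departs from the fitted pooled variance; some unequal profiles leave it almost unchanged.
- A reader might infer that early-week SD must be lower, since baseline scores lie between 5.0 and 9.8 (five items averaged, so steps of 0.2) and their SD cannot exceed (9.8 − 5.0)/2 = 2.4, against a planned 3. These are different quantities: a bound on the baseline score and a planning SD for change at Week 12. The fallback pools residual variance after adjustment for baseline, region and gender. Baseline imputation, moreover, points towards a conservative test.
- A reader might infer that the plan omits a robust SE. The supplied text is a synopsis, and the SAP to which it defers may already specify one.

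It is also true that the fixed order leaves the analyst no choice of structure. That protects against selection but does not make the SE right.

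**Conclusion.** The point holds as a conditional weakness and a cheap improvement, not as a demonstrated error. The fallback order is fixed in the protocol synopsis, and each fallback as named has a common variance. Whether this matters depends on UN failing and on weekly residual SDs that the documents do not give. The direction is therefore unknown and the tabulated sizes are only a range under assumed profiles, with large-sample theory and complete data except in the dropout simulation. Unequal variance is not the only route to a wrong SE either: with dropout, a wrong correlation structure may contribute too. Severity is low; this is a change the sponsor could make.

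**What to change.** Keep UN first and keep the existing fallback order, ending at plain CS. Add to Section 1.5.3, or confirm that the SAP already states:

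> Whenever a structured covariance matrix is used, empirical (sandwich) standard errors with between-subject degrees of freedom will be used for the treatment comparison.

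Optionally, try the heterogeneous versions of TOEP, AR(1) and CS before the plain ones, with plain CS plus sandwich SE as last resort.

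The cost is one sentence and a few lines of code, settled before unblinding. SEs become slightly noisier, which is minor at 225 per arm. Apparent power falls where the model-based SE was too small: in the simulation with SD 2.5 to 3, from 94% to 90% (CS) and from 91% to 88% (AR(1)). With SD 3.5 to 3 under CS, it went from 88.8% to 90.0%. The sandwich SE does not correct a shift in the estimate caused by a wrong covariance with missing data: under the assumed dropout, a true 1-point effect was estimated as 0.95 to 1.03.
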